10.3 HANDLING PROCEDURES FOR BLOOD SAMPLES FOR PLASMA CONCENTRATION-TIME MEASUREMENTS

Handling procedures for blood samples are presented in the Laboratory Manual.

10.4 TIME SCHEDULES FOR PHARMACOKINETIC, BIOMARKER, AND IMMUNOGENICITY BLOOD SAMPLING

10.4.1 Schedules for PK, biomarker, and immunogenicity blood sampling – Phase Ia (dose escalation) cohorts

Table 10.4.1: 1

Time schedule for PK, biomarker [REDACTED]
blood sampling during Cycles 1, 2, and 4 - Phase Ia dose-escalation cohorts

Treatment Cycles	Day	Time Point [hh:min]	CRF Time	Event	PK	[REDACTED]	[REDACTED]
1, 2, 4	1	Just before start of infusion	-0:05	Blood sampling	X	X	X
		0:00	0:00	Start of BI 754091 infusion	---		
		Sampling during infusion	0:30	Blood sampling	X		
		Immediately before end of infusion*	1:00	Blood sampling	X		
		1.5 hours post SOI	1:30	Blood sampling	X		
		2 hours post SOI	2:00	Blood sampling	X		
		4 hours post SOI	4:00	Blood sampling	X		
	2	7 hours post SOI	7:00	Blood sampling	X		
		24 hours post SOI	24:00	Blood sampling	X		X
		4	72 hours post SOI	72:00	Blood sampling	X	
EOT	8	168 hours post SOI	168:00	Blood sampling	X		X
	15	336 hours post SOI	336:00	Blood sampling	X		
30-Day FU		Within 7 days of treatment discontinuation		Blood sampling	X	X	
		30 days after last drug administration		Blood sampling	X	X	X

ADA = anti-drug antibodies; BI = Boehringer Ingelheim; CRF = Case Report Form; EOT = end of treatment; FU = follow up; PK = pharmacokinetics; [REDACTED]

*In the event that infusion duration is >15 minutes longer than planned, the subsequent time points for PK blood collection on the day of drug infusion should be adjusted accordingly.

Proprietary confidential information © 2023 Boehringer Ingelheim International GmbH or one or more of its affiliated companies

Table 10.4.1: 2

Time schedule for PK, biomarker [REDACTED]
blood sampling during Cycles 3, 5 through 12, 14, 17, EOT (end-of-treatment visit) and 30-day FU (follow-up visit) - Phase Ia dose-escalation cohorts

Treatment Cycles	Day	Time Point [hh:min]	CRF Time	Event	PK	[REDACTED]	[REDACTED]
3, 5 to 12, 14, and 17	1	Just before start of infusion	-0:05	Blood sampling	X	X	X
		0:00	0:00	Start of BI 754091 infusion	---		
		Immediately before end of infusion	1:00	Blood sampling	X		
EOT				Blood sampling	X	X	
30-day FU				Blood sampling	X	X	X

ADA = anti-drug antibodies; BI = Boehringer Ingelheim; CRF = Case Report Form; EOT = end of treatment; FU = follow up; PK = pharmacokinetics; [REDACTED]; only done during dose escalation, if feasible)

**10.4.2 Schedules for PK, biomarker, and immunogenicity blood sampling –
Phase Ib (dose expansion) - All Cohorts**

Table 10.4.2: 1

Time schedule for PK, biomarkers

blood sampling in all Phase Ib dose-expansion cohorts

Treatment Cycles	Day	Time Point [hh:min]	CRF Time	Event	PK**		Cytokines*	
1, 4, 8	1	Just before start of infusion	-0:05	Blood sampling	X	X	X (C1)	X (C1)
		0:00	0:00	Start of BI 754091 infusion	---			
		Shortly after end of infusion	1:00	Blood sampling	X			
	2	24 hours post SOI	24:00	Blood sampling			X (C1)	
	8	168 hours post SOI	168:00	Blood sampling	X		X (C1)	X (C1)
2, 3, 5-7, 9	1	Just before start of infusion	-0:05	Blood sampling	X	X	X (C2)	X (C2)
		0:00	0:00	Start of BI 754091 infusion	---			
	1	Just before start of infusion	-0:05	Blood sampling	X	X		
Thereafter every 3 rd cycle (12, 15, 18, etc)		0:00	0:00	Start of BI 754091 infusion	---			
EOT				Blood sampling	X ¹	X ¹	X ¹	X ¹
30-day FU				Blood sampling	X ¹	X ¹		

ADA = anti-drug antibodies; BI = Boehringer Ingelheim; CRF = Case Report Form; EOT = end of treatment; FU = follow up; [REDACTED]; PK = pharmacokinetics

* [REDACTED] for flow analysis are only collected during the dose expansion phase on Cycle 1 Day 1 (pre-dose), Day 2 (cytokines only), Day 8, Day 15, Cycle 2 Day 1 (pre-dose), and end of treatment

**The following windows of time are allowed for PK sampling:

Predose (PTM -0:05): within 1 hour before next drug infusion

Shortly after end of infusion (PTM 1:00): within 5 min after the end of infusion

24 through 336 hours post SOI (PTM 24:00 to 336:00): ±1 hour.

Note: Time windows have been specified for procedural reasons; deviations do not automatically lead to exclusion of samples from data evaluation.

¹ Only patients completed this activity up to until the cut off date for the primary report.

10.5 STATISTICAL APPENDIX INCLUDING MODEL PERFORMANCE AND DATA SCENARIOS

A BLRM with overdose control will be used to guide dose escalation in this study. The BLRM is introduced in Section 7.1.1, which also specifies the prior for the model. After patients in each cohort have completed at least one cycle of treatment, the prior distribution will be updated through Gibbs sampling procedures with the accumulated DLT data from the MTD evaluation period (first three weeks). Posterior probabilities for the rate of DLTs will be summarised from BLRM. Selection of the next dose will be based on these probabilities as well as on other safety and laboratory data.

The purpose of this statistical appendix is to present performance metrics (operating characteristics) that illustrate the precision of the design in estimating the MTD under various dose-toxicity relationships through computer simulation. These results are summarized in [Table 10.5.2: 1](#). In addition, recommendations for the next dose level by the BLRM with overdose control principle are also provided under various hypothetical outcome scenarios in early cohorts to show how EWOC facilitates on-trial dose-escalation decisions (see [Table 10.5.2: 2](#)). For simplicity reasons, a cohort size of 3 patients who are all evaluable is assumed. The simulations for scenarios and operating characteristics were produced using RStudio version 0.98.507.

10.5.1 Hypothetical data scenarios

Hypothetical data scenarios are shown in [Table 10.5.1: 1](#). These scenarios reflect potential on-study data constellations and related escalation as allowed by the model. It is assumed that each cohort has exactly 3 patients who are all evaluable. For each scenario, the probability of overdose for the current dose, as well as the next potential dose and related probabilities of under-dosing, target dose, and over-dosing are shown.

For example, Scenario 1 represents the case that no DLT is observed in the first 3 patients at the starting dose of 80 mg. In this case, the next optimal dose, i.e., the dose with the highest probability of being in the target interval, is 800 mg. However, to have the next dose level at 800 mg seems too aggressive and thus the recommended dose for next level should be provided by the SRC.

Scenario 2 represents the case that no DLTs are observed in both the 80 mg and the 240 mg cohorts with 3 patients in each cohort. The probabilities of each dose level under both target-dose and over-dose range are lower than the probabilities in Scenario 1 as expected.

Scenario 3 represents the case that no DLTs are observed in the first 3 patients at the starting dose of 80 mg but there is one DLT in the next dose level, 240 mg. In this case, the next optimal dose is 320 mg which has the highest probability in the target dose level. However, it will be SRC's decision whether to have another cohort tested at dose 240 mg or to increase the dose level to 320 mg, since one DLT was observed at the dose level of 240 mg.

Table 10.5.1: 1 Hypothetical data scenarios

Scenario	Dose (mg)	# DLT	# Pat	Current Dose: P(OD)	Next Recommended Dose (mg)	Next optimal dose		
						P(under dose)	P(target dose)	P(over dose)
1	80	0	3	0.001	800	0.898	0.054	0.047
2	80 240	0 0	3 3	0	800	0.919	0.047	0.034
3	80 240	0 1	3 3	0.186	320	0.506	0.247	0.247
4	80 240	0 1	3 6	0.031	560	0.541	0.247	0.212
5	80 240 400	0 1 0	3 6 3	0.033	800	0.613	0.217	0.170
6	80 240 400	0 1 1	3 6 3	0.195	400	0.406	0.399	0.195

*non-DLT drug-related AE of CTCAE grade ≥ 2

**Overdose-probability of the next optimal dose is too high (violates EWOC criterion), therefore the maximal allowed dose would be chosen as next dose by the model.

10.5.2 Operating Characteristics

Operating characteristics are a way to assess the long-run behaviour of a model. Under an assumed true dose-toxicity curve, metrics such as the probability of recommending a dose with true DLT rate in the target interval can be approximated via simulation. Table 10.5.2: 1 describes 4 assumed true dose-toxicity scenarios which were used to assess the operating characteristics of the model. These scenarios reflect a wide range of possible cases. Scenarios 1 and 2 reflect the extremes of very low and very high toxicity probabilities, respectively. Scenario 3 covers a true dose-toxicity relationship that does not have a logistic form. Finally, Scenario 4 reflects the possibility of having very low DLT rates at the lower dose levels and high DLT rates at the upper dose levels. Scenario 1 is more similar to the prior distribution of this trial. The stopping rule is the same as the MTD criteria mentioned in Section 7.1.1.

Table 10.5.2: 1 Assumed True Dose-Toxicity Scenarios

Scenario	Dose (mg)						
	80	160	240	320	400	480	3200
1: Low Tox	0.00001	0.0005	0.009	0.013	0.028	0.050	0.160
2: High Tox	0.050	0.097	0.140	0.180	0.249	0.309	0.359
3: Non-Logistic	0.001	0.0102	0.0397	0.1795	0.220	0.269	0.339
4: Low-High	0.001	0.040	0.180	0.280	0.360	0.380	0.500

Bold numbers indicate true DLT rates in the target interval [0.16, 0.33].

For each of these scenarios, 1000 trials were simulated. It was then assessed how often a dose was declared as MTD with true DLT rate in the under-, targeted-, or over-dose range. Furthermore, the average, minimum and maximum number of patients per trial and the average number of DLTs per trial are reported. Results are shown in [Table 10.5.2: 2](#).

Table 10.5.2: 2 Simulated Operating Characteristics

Scenario	% of Trials Declaring an MTD with True DLT Rate in				# Patients	# DLT
	Underdose	Target dose	Overdose	Stopped Before MTD		
1: Low Tox	94.0	0	0	6.0	25.36 (12-60)	1.011 (0-4)
2: High Tox	16.7	83.3	0	0	17.18 (3-42)	3.152 (1-11)
3: Non-Logistic	4.5	95.5	0	0	16.03 (12-39)	2.48 (1-9)
4: Low-High Tox	6.7	46.0	47.3	0	17.83 (6-42)	3.78 (1-11)

In Scenario 1 (low-toxicity scenario), since none of the assumed true dose-toxicity scenarios were beyond 16%, 94% of the simulated trials declared a dose as MTD with true DLT rate in the under dose range. 6% of the trials stopped before MTD was reached and this is because the very low-toxicity level to allow a trial stop before reaching an MTD. For Scenario 2 (high-toxicity scenario), 83.3% of the simulated trials declared an MTD with true DLT rate in the target dose range. This is an expected situation as assumed dose-toxicity scenarios at 320 mg, 400 mg, and 480 mg lie within the target dose level. Results of Scenario 3 (high-toxicity scenario) are very close to the results of Scenario 2 as the setting for the high-dose

level is similar between these two scenarios. Results of Scenario 4 (Low-High scenario) show ~50% of the simulated trials declared a dose as MTD with true DLT rate in both the targeted dose range and also overdose range. This is because in the setup, assumed true dose-toxicity rates at 400 mg, 480 mg, and 320 mg were above 33%.

The mean patient numbers range from 16.03 (Scenario 3) to 25.36 (Scenario 1) and only Scenario 1 had the maximum of 60 patients. The patient numbers are as expected and decrease when moving away from the low-toxicity scenario. In summary, the considered data scenarios show a reasonable behaviour of the model and the operating characteristics demonstrate a good precision of MTD determination.

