4.1.6 Definition of maximum-tolerated dose

The MTD may be considered reached if at least one DLT is observed in the trial and one of the following criteria is fulfilled:

- The posterior probability of the true DLT rate in the target interval [0.16 – 0.33) of the MTD is above 0.50

OR

- At least 15 patients have been treated in the trial, of which at least 6 have been treated at the MTD.

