7.1.1 Statistical design – Phase Ia (dose escalation)

The objective of the Phase Ia portion of the trial is to determine the MTD and the RP2D. The MTD is defined as the highest dose with less than 25% risk of the true DLT rate being above 0.33 (EWOC criterion) under the condition of at least one DLT observed in this trial. The Phase Ia dose-finding will be guided by a BLRM with overdose control (R13-4803).

The model is given as follows:

$$\text{logit}(p(d)) = \log(\alpha) + \beta * \log(d/d^*),$$

where $\text{logit}(p) = \log(p/(1-p))$.

$p(d)$ represents the probability of having a DLT in the first cycle at dose d , $d^* = 800$ mg is the reference dose, allowing for the interpretation of α as the odds of a DLT at dose d^* , and $\theta = (\log(\alpha), \log(\beta))$ with $\alpha, \beta > 0$ is the parameter vector of the model.

The estimated probability of a DLT at each dose level from the model will be summarized using the following intervals:

Under dosing: [0.00, 0.16)
Targeted toxicity: [0.16, 0.33)
Over toxicity: [0.33, 1.00]

The BLRM recommended dose for the next cohort is the level with the highest posterior probability of the DLT rate falling in the target interval [0.16, 0.33) among the doses fulfilling EWOC. Applying the EWOC criterion it should be unlikely (<25% posterior probability) that the DLT rate at that dose will exceed 0.33.

The MTD may be considered reached if one of the following criteria is fulfilled:

- At least one DLT observed in the trial, and either
- The posterior probability of the true DLT rate in the target interval [0.16 – 0.33) of the MTD is above 0.50, OR
- At least 15 patients have been treated in the trial, of which at least 6 at the MTD.

The SRC may recommend stopping the dose-finding phase after the criteria for MTD are fulfilled. If no DLTs are observed during the Phase Ia dose-escalation phase, the SRC may conclude that the MTD was not found and decide to include an additional number of patients at a dose of which the efficacy is considered sufficient as the dose recommended for further testing. This dose level may be equal or below the highest tested dose level.

Since a Bayesian approach is applied, a prior distribution $\pi(\theta)$ for the unknown parameter vector θ needs to be specified. This prior distribution will be specified as a mixture of two multivariate normal distributions, i.e.

$$\pi(\theta) = \varphi_1 \pi_1(\theta) + \varphi_2 \pi_2(\theta)$$

with

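### Table 10.5.2:2, Scenario 2 reports no trial stopped before an MTD, yet a minimum of 3 patients, which cannot satisfy the MTD criteria; the 83.3% success figure is overstated by roughly 3 points

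*Protocol*

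**What the plan says.** Section 10.5.2 simulates 1000 trials per scenario. On stopping it says: "The stopping rule is the same as the MTD criteria mentioned in Section 7.1.1". Section 7.1.1 (repeated in Section 4.1.6) requires at least one DLT plus one of two conditions:

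- the posterior probability of the target interval exceeds 0.50 at the candidate dose; or
- "At least 15 patients have been treated in the trial, of which at least 6 at the MTD".

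The next dose is the one with the "highest posterior probability of the DLT rate falling in the target interval [0.16, 0.33) among the doses fulfilling EWOC". EWOC means that "it should be unlikely (<25% posterior probability) that the DLT rate at that dose will exceed 0.33".

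For Scenario 2 (High Tox), Table 10.5.2:2 prints underdose 16.7, target 83.3, overdose 0, stopped before MTD 0, patients 17.18 (3–42) and DLTs 3.152 (1–11). The text repeats that "83.3% of the simulated trials declared an MTD with true DLT rate in the target dose range". It concludes that the operating characteristics show good precision of MTD determination.

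**The concern.** The four percentages in the Scenario 2 row say that every trial declared an MTD. The minimum of 3 in the same row says that at least one trial ended after a single cohort. Under the quoted rule both cannot be true.

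The stopped-before-MTD column is used elsewhere: Scenario 1 shows 6.0% there. A reader comparing rows will conclude that the design never stops for toxicity without an MTD in the high-toxicity case, although the true DLT rate at the 80 mg starting dose is set at 5%. The frequency of such stops is an operating characteristic in its own right. Leaving it out also raises the correct-selection figure that supports the claim of good precision.

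**Working it through.** **Inputs.** From Section 7.1.1.1: a two-component prior with weights 0.9 and 0.1, means (−4.855, 1.062) and (−0.578, 0.028), SDs (2, 1) and correlation 0. From Section 7.1.1: reference dose 800 mg, and the EWOC limit and MTD criteria quoted above. From Section 10.5: cohorts of 3, all evaluable. From Table 10.5.2:1: Scenario 2 true rates 0.05, 0.097, 0.14, 0.18, 0.249, 0.309 and 0.359 at 80, 160, 240, 320, 400, 480 and 3200 mg. The posterior was computed by numerical integration on a grid.

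**The plan's own figures.** 16.7 + 83.3 + 0 + 0 = 100, so the row leaves no room for a stopped trial. As a model check, data scenario 6 of Table 10.5.1:1 gives P(overdose) 0.195 at 400 mg, as printed. Data scenarios 1, 2, 4 and 5 agree to within about 0.02; data scenario 3 is not reproduced.

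**Can 3 patients meet the MTD criteria?** The 15-patient condition fails at once. Posterior after one cohort at 80 mg:

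| DLTs | P(target) at 80 mg | P(overdose) at 80 mg | Probability at true rate 0.05 |
|---|---|---|---|
| 0/3 | 0.006 | 0.002 | 0.8574 |
| 1/3 | 0.25 | 0.245 | 0.1354 |
| 2/3 | 0.19 | 0.73 | 0.0071 |
| 3/3 | 0.03 | 0.96 | 0.0001 |

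The largest P(target) after any of these outcomes, at any dose checked from 20 to 3200 mg, is about 0.26, so the 0.50 condition fails too. With 2/3 or 3/3 even the lowest simulated dose exceeds the 25% limit, and so does every higher one. Such a trial ends with no admissible dose and no MTD.

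**How often in Scenario 2?**

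- At N = 3: P(at least 2 of 3) = 3 × 0.05² × 0.95 + 0.05³ = 0.00725. Over 1000 trials, the chance of at least one is 1 − (1 − 0.00725)^1000 = 0.9993.
- At N = 6, via 80 mg twice: after 1/3, only 80 mg is admissible. One more DLT gives 2/6, where P(overdose) is 0.33. Probability: 0.1354 × (1 − 0.95³) = 0.1354 × 0.1426 = 0.0193.
- These two paths sum to 0.00725 + 0.0193 = 2.7% and do not depend on any step limit.
- Other paths depend on the step limit. Exact enumeration gives 3.0% in total with a 3-fold limit, 3.4% with a 2-fold limit, and 3.0–3.5% over all variants. Adding Monte Carlo noise of 5,000–20,000 posterior draws gives 3.5–5.4%, because 1/3 at 80 mg lies just under the limit.
- At a rate of 3.3%, the chance of no stop in 1000 trials is 0.967^1000, about 3 × 10⁻¹⁵.

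**Effect on the 83.3%.**

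| Step limit (assumed) | Underdose | Target | Stopped | Target among declared |
|---|---|---|---|---|
| 3-fold | 17.1% | 79.9% | 3.0% | 82.4% |
| 2-fold | 16.1% | 80.5% | 3.4% | 83.3% |

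Across variants the target share of all trials is about 78–82%. Against a central 80%, 83.3 − 80 = 3.3 points.

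**Scenario 4.** The row prints a minimum of 6 patients and 0% stopped. No six-patient outcome starting from 80 mg gives P(target) above about 0.38 at a simulated dose, so a 6-patient trial cannot meet the criteria either. Under a 3-fold step, 0/3 at 80 mg followed by 3/3 at 240 mg bars every dose. Its probability is 0.999³ × 0.18³ = 0.6%.

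**The case against.** **The stop for no admissible dose is not written down.** True. It follows from EWOC combined with a simulated grid that starts at 80 mg; Section 10.5.2 names only the MTD criteria. The natural alternative is that simulated trials continued at 80 mg. That removes the stops, but the minimum sample size becomes 12, which contradicts the printed 3. If the 3 is itself a misprint, the row still needs correcting.

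**The sponsor's program has not been reproduced.** This also stands. Step limits and the minimum number at a dose are not given. Scenarios 1 and 3 are closely matched with a 3-fold step (93.9% underdose and 6.1% undeclared; 4.3/95.6). However, the recalculated maximum sample size in Scenario 2 is 30–36 against the printed 42. The percentages here show the size of the problem and cannot replace the printed ones.

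**A reader might infer that the stopped trials were left out of the denominator.** The 82.4–83.3% among declared trials is consistent with that. Counting the stopped trials as target fits as well: 79.9 + 3.0 = 82.9%. The documents do not say which was done.

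**A reader might also infer that the table conceals how often the drug would be abandoned.** The protocol does not support this. Section 3.1 sends early DLTs to a model re-run and a committee decision on the same or a lower dose, and Section 4.1.3 allows lower levels. The 80 mg floor is a feature of the simulation.

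**The effect is small.** Agreed. The simulation standard error is √(0.833 × 0.167/1000) = 1.2 points. No sample size or analysis uses the figure, and the SAP (Section 4) treats Phase Ia grading as completed. Scenario 4's printed 47.3% overdose bears more heavily on the precision claim.

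**Conclusion.** Wrong as written, of minor severity. The contradiction between a minimum of 3 patients and 0% stopped before MTD rests only on the stated prior, the stated criteria and the printed row. The size is approximate: about 3% of Scenario 2 trials stopped with no admissible dose, and about 78–82% of all trials with an MTD in the target range, so 83.3% is too high by roughly 3 points. That size assumes the 80 mg grid floor, cohorts of 3, a 60-patient cap (the largest trial size Section 10.5.2 reports) and the step limits tried. Scenario 4 shows the same conflict on a smaller scale. How the stopped trials were tabulated cannot be determined from the documents.

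**What to change.** Re-tabulate Table 10.5.2:2 from the sponsor's archived simulation output, or from a rerun:

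- use all 1000 trials as the denominator in every row;
- count trials with no EWOC-admissible dose under 'Stopped Before MTD';
- check Scenario 4 in the same way as Scenario 2;
- correct the 83.3% sentence in Section 10.5.2;
- state there how the simulation treated a trial with no admissible dose, and which step limits it used.

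The percentages in this note should not be inserted as the sponsor's results. The cost is one or two table rows, one corrected sentence and one added sentence, plus a rerun if the output was not kept. Nothing in the conduct or analysis of the trial changes.

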11. DESCRIPTION OF GLOBAL AMENDMENTS

Number of global amendment	1
Date of CTP revision	01 November 2016
EudraCT number	Not applicable
BI Trial number	1381.1
BI Investigational Product	BI 754091
Title of protocol	An open-label, Phase I trial to determine the maximum-tolerated dose and investigate safety, pharmacokinetics, and efficacy of BI 754091 in patients with advanced solid tumours
To be implemented only after approval of the IRB / IEC / Competent Authorities	
To be implemented immediately in order to eliminate hazard – IRB / IEC / Competent Authority to be notified of change with request for approval	
Can be implemented without IRB / IEC / Competent Authority approval as changes involve logistical or administrative aspects only	
Additions to the text are bolded and deletions from the text are crossed off . Please note that formatting changes and minor changes to punctuation or spelling that do not affect meaning are not noted in this summary.	
Section to be changed	Synopsis: Main criteria for inclusion
Description of change	Phase Ia (dose escalation) – adult patients with a confirmed diagnosis of advanced, unresectable, and/or metastatic solid tumours (any type) who have received all therapy known to confer clinical benefit (including anti-PD-1 therapies, if relevant and if last dose of the prior anti-PD-1 received more than 60 days prior to starting study drug), or for whom no therapy of proven efficacy exists, or who are not amenable to standard therapies
Rationale for change	In response to the FDA review, the decision was made to allow patients who had received previous treatment with an anti-PD-1 therapy to enter the dose-escalation phase (Part 1a) of the trial.
Section to be changed	Synopsis: Main criteria for inclusion

Description of change	Phase Ib (dose expansion) – adult patients with a confirmed diagnosis of select advanced, unresectable, and/or metastatic solid tumours (non-small cell lung cancer, bladder cancer, melanoma, gastric cancer, ovarian cancer, triple-negative breast cancer [TNBC], or renal cell carcinoma) Patients who are anti-PD-1 naïve, but have failed conventional treatment (excluding anti-PD-1 treatment), or for whom no therapy of proven efficacy exists, or who are not amenable to standard therapies
Rationale for change	Clarification that patients in the dose-expansion portion (Part 1b) of the trial still must be naïve to anti-PD-1 therapy.
Section to be changed	Flow Chart Footnote d (third sentence)
Description of change	If these assessments are performed within 72 hours of initiation of treatment, they do not need to be repeated on Cycle 1 Day 1 with the exception of the ECOG performance status, an abbreviated physical examination, vital signs (pre- and post-infusion), and a single ECG required prior to first trial dose.
Rationale for change	To clarify this requirement for the sites.
Section to be changed	Flow Chart and Footnote k
Description of change	The collection of optional DNA banking samples was removed from the protocol. All footnotes following Footnote k were reordered.
Rationale for change	Optional DNA banking has been removed as the number of samples is not anticipated to be enough to provide significant benefit to the patients or the sponsor.
Section to be changed	Flow Chart Footnote i, Section 5.5.2.1, and footnotes of Tables 10.4.1: 1 and 10.4.1: 2
Description of change	Blood samples for biomarkers [REDACTED] will be collected (if feasible)
Rationale for change	To clarify that this test may not be done.
Section to be changed	Flow Chart 1 Footnote k, Flow Chart 2 Footnote l, Section 5.5.2.3
Description of change	Stable disease over 3 subsequent measurements would also be qualified as a response, and a biopsy (optional) would be taken at that time point. An optional biopsy should also be taken if a patient has stable disease over 3 subsequent disease assessment periods.
Rationale for change	Clarification
Section to be changed	Section 3.1 Overall trial design and plan
Description of change	Successive cohorts of patients will receive doses of BI 754091 until the MTD is reached. A cohort size of 3 patients will be treated at each dose level. Additional patients (up to 6 more) could be added to some previously evaluated cohorts to expand the safety and PK evaluation. At least 3 patients will be required for any dose escalation cohort (refer to Section 7).

	
A Safety Review Committee (SRC, see Section 3.1.2) may also recommend the size for the next dose escalation cohort. However, the final decision on the next cohort size will be made mutually between the BI Clinical Program Leader and the SRC. After all patients in a cohort have either experienced a DLT or have been observed for at least the MTD evaluation period (first 3 weeks) without experiencing a DLT, the Bayesian model will be updated with the newly accumulated data. The overdose risk will then be calculated for each dose, and escalation will be permitted to all doses which fulfil the EWOC criterion. Hypothetical data scenarios (example in Section 10.5.1) will be calculated with potential cohort sizes and presented at the meetings with the Safety Review Committee (SRC, see Section 3.1.2). Based on the model and on additional information (PK, pharmacodynamics [PDc], patient profiles), the members of the SRC will reach a joint decision recommendation on the next dose level to be investigated and the size for the next dose-escalation cohort. However, the final decision on the next dose level and cohort size will be made mutually between the BI Clinical Program Leader and the SRC.

Rationale for change	In response to the FDA review, clarification was added on how the number of patients per dose level will be determined during dose escalation.
Section to be changed	Section 3.3.2 Inclusion Criterion #4
Description of change	
Phase 1a (dose escalation) – patients who have received all therapy known to confer clinical benefit (including PD-1 therapies, if relevant), or for whom no therapy of proven efficacy exists, or who are not amenable to standard therapies. Patients with PD-1 experience must have a minimum of 60 days between the last dose of the previous PD-1 and Cycle 1 Day 1 of BI 754091 treatment. Phase 1b (dose expansion) – patients who are anti-PD-1 naïve but have failed conventional treatment (excluding anti-PD-1 treatment), or for whom no therapy of proven efficacy exists, or who are not amenable to standard therapies.

Rationale for change	In response to the FDA review, the decision was made to allow patients who had received previous treatment with an anti-PD-1 therapy to enter the dose-escalation phase (Part 1a) of the trial. Patients must still be naïve to anti-PD-1 therapies in order to enter the dose-expansion phase.
Section to be changed	Section 3.3.2 Inclusion Criterion #8
Description of change	Females of child-bearing potential willing to use adequate contraceptive measures from the time of screening until 6 months after trial discontinuation, who are not or will not be breast feeding, and agree to have pregnancy tests prior to the start of dosing and at regular visits during the trial. Females not of childbearing potential must have evidence of such by fulfilling one of the following criteria at screening:

Proprietary confidential information © 2023 Boehringer Ingelheim International GmbH or one or more of its affiliated companies

	
 - Post-menopausal: defined as more than 50 years-of-age and amenorrhoeic for at least 12 months following cessation of all exogenous hormonal treatments - Documentation of irreversible surgical sterilization by hysterectomy, bilateral oophorectomy, or bilateral salpingectomy, but not tubal ligation.
Rationale for change	The sponsor considers tubal ligation as a highly effective form of birth control and the current ICF text reflects this.
Section to be changed	Section 4.1.5 Definition of dose-limiting toxicity
Description of change	
 • Any \geqGrade 3 non-haematologic toxicity with the following exceptions: 
 - Grade 3 irAE that resolves to \leq Grade 1 or to baseline with immunosuppressive therapy within 23 weeks - Grade 3 rash that resolves to \leq Grade 1 within 23 weeks - Grade 3 infusion reaction that resolves within 6 hours to \leq Grade 1 with the appropriate clinical management
Rationale for change	Exceptions were updated to reflect FDA feedback.
Section to be changed	Section 4.1.5 Definition of dose-limiting toxicity
Description of change	
Late immune-related DLTs are irAEs that meet the same grading criteria as DLT criteria but occur after the initial 21-day DLT period and during the first 90-day assessment period. These, as well as all toxicities, will be monitored throughout the trial. If any late immune-related DLT is reported during dose-escalation, the BLRM will be rerun including the late immune-related DLT, and updated results will be reviewed in the SRC meeting to recommend the next dose level and cohort size.

Rationale for change	In response to the FDA review, text was added to clarify how information on late immune-related DLTs will be used in making dosing (or other) decisions during the trial.
Section to be changed	Section 5.3.1 Physical examinations and ECOG performance status
Description of change	The ECOG score will be assessed at screening, on Day 1 of Cycles 1 and 2, on Day 1 of every other cycle beginning with Cycle 3 treatment cycle prior to trial medication intake, at the EOT visit, and at the 30-day safety follow-up visit.
Rationale for change	To clarify this statement for the sites and to align with the Study Flow Footnote e.
Section to be changed	Section 5.3.6.3 Definition of serious adverse events
Description of change	is to be deemed serious for any other reason if it is an important medical event when based upon appropriate medical judgment which may jeopardise the patient and may require medical or surgical intervention to prevent one of the other outcomes listed in the above definitions.

	
Medical and scientific judgement should be exercised in deciding whether other situations should be considered serious reactions, such as important medical events that might not be immediately life threatening or result in death or hospitalisation, but might jeopardise the patient or might require intervention to prevent one of the other outcomes listed above. Examples of such events are intensive treatment in an emergency room or at home for allergic bronchospasm, blood dyscrasias or convulsions that do not result in hospitalisation or development of dependency or abuse.
 
Any suspected transmission via a medicinal product of an infectious agent is also considered an SAE.

Rationale for change	Corrected to align with the sponsor's accepted safety language.
Section to be changed	Section 5.3.6.5.3 Infusion-related reactions
Description of change	If an the infusion-related reaction is Grade 3 or higher in severity at any point during the study , treatment with BI 754091 will be permanently discontinued.
Rationale for change	In response to the FDA review, this statement was clarified.
Section to be changed	Section 5.3.6.5.4 Hepatic injury and D drug-induced liver injury (DILI)
Description of change	
During the course of the trial the Investigator will remain vigilant for increases in liver biochemistry. The Investigator is responsible for determining whether a patient meets the hepatic injury definition or potential Hy's Law criteria at any point during the trial.
 
The Investigator participates, together with the Medical Monitor and BI clinical project representatives, in review and assessment of cases meeting potential hepatic injury and Hy's Law criteria. Hy's Law criteria are met if there is no alternative explanation for the elevations in liver biochemistry other than a DILI caused by the investigational product.
 
Hepatic injury definition: In patients with normal baseline hepatic function, hepatic injury is defined by the following alterations in hepatic laboratory parameters:
 
 • An elevation of AST and/or ALT ≥ 3 times the ULN combined with an elevation of total bilirubin ≥ 2 times the ULN measured in the same blood draw sample. And/or • Marked peak AST and/or ALT elevation ≥ 10 times the ULN.
Rationale for change	To clarify potential liver injury by including hepatic injury definitions in addition to the definition of Hy's Law criteria.
Section to be changed	

Description of change	
Rationale for change	
Section to be changed	Section 5.5.3 Biobanking
Description of change	
At the Cycle 1 Day 1 visit, one 8.5 mL blood sample for DNA banking will be collected in a PAXgene Blood DNA tube for those patients in either portion of the trial who agree by checking the appropriate box in the ICF. The DNA Banking sample, derived from the original blood sample, will be stored at the sponsor. The stored DNA may retrospectively be analysed, e.g., to identify whether there are other genetic factors that could contribute to a better therapeutic outcome or a higher risk of developing treatment related adverse drug reactions.
 
Note: Participation in the DNA banking sampling and the long-term storage and use of leftover samples is voluntary and not a prerequisite for participation in the trial. The biological samples to be banked will be stored after the appropriate separate boxes are checked on the ICF by consenting patients in accordance with local ethical and regulatory requirements.

Rationale for change	Optional DNA banking has been removed as the number of samples is not anticipated to be enough to provide significant benefit to the patients or the sponsor.
Section to be changed	Section 5.5.3 Biobanking
Description of change	Any leftover samples (including tissue, plasma, serum, ADA, DNA, RNA, etc.) from the trial may be stored at the sponsor or an external biobanking facility on behalf of the sponsor for up to 30 years.
Rationale for change	ADA samples will be stored as per Section 5.6.1
Section to be changed	Section 8.4 Expedited reporting of adverse events
Description of change	BI is responsible to fulfil their legal and regulatory reporting obligation in accordance with regulatory requirements.
Rationale for change	For clarification purposes.

Section to be changed	Section 10.2 Management of immune-related (only parts that changed are presented)
Description of change	Management of immune-related event toxicities associated with anti-PD-1 mAbs are presented below . BI 754091 should be permanently discontinued for Grade 3-4 pneumonitis, Grade 3-4 adrenal insufficiency, Grade 4 diabetes mellitus, any grade encephalitis, Grade 4 hypophysitis, Grade 4 rash, Grade 3-4 or recurrent colitis of any grade, any recurrent Grade 3-4 AE, transaminase >5 times ULN or total bilirubin >3 times ULN, inability to taper steroids to 10 mg or less prednisone or equivalent within 12 weeks, or persistent Grade 2-3 AEs that do not recover to Grade 1 or less within 12 weeks.
Description of change	
• Pneumonitis:
- BI 754091 should be permanently discontinued for Grade 3-4 pneumonitis, inability to taper steroids to 10 mg or less prednisone or equivalent within 12 weeks, or persistent Grade 2 AEs that does not recover to Grade 1 or less within 12 weeks.
Description of change	
• Diarrhoea/Colitis:
- For Grade 3 or 4 diarrhoea/colitis that persists >1 week, treat with i.v. steroids followed by high-dose oral steroids.
- For Grade 3 or 4 colitis, or recurrent colitis of any grade, permanently discontinue BI 754091 and immediately treat with i.v. steroids followed by high-dose oral steroids.- BI 754091 should be permanently discontinued for Grade 3-4 or recurrent colitis of any grade, inability to taper steroids to 10 mg or less prednisone or equivalent within 12 weeks, or persistent Grade 2-3 AEs that do not recover to Grade 1 or less within 12 weeks.
